9.5.1.2 Duration of Response

Kaplan-Meier methods will be used to estimate the distribution of DOR. And the median and other quartiles in addition to the corresponding two-sided 95% confidence intervals will be calculated.

A Kaplan-Meier figure showing the estimated DOR distribution will be provided.

9.5.1.3 MRD Negativity at CR

MRD negativity analysis will be performed for all subjects included in the safety analysis set. Number of MRD[-] responders at CR along with exact 2-sided 95% will be provided by using Clopper & Pearson method

9.5.2 Analyses of Secondary Efficacy Endpoint(s)

9.5.2.1 Progression-free Survival

PFS analysis will be performed for all subjects included in the safety analysis set. The Kaplan-Meier curve will be generated. PFS rate at 3-month intervals and the median and other quartiles in addition to the corresponding two-sided 95% confidence intervals will be provided. Disease progression determined by using IMWG-URC will be used for the analysis.

9.5.2.2 Overall Survival

OS analysis will be performed for all subjects included in the safety analysis set. **The Kaplan-Meier curve will be generated.** Overall survival rate at 3-month intervals, the median and other quartiles in addition to the corresponding two-sided 95% confidence intervals will be calculated.

[figure not shown]
9.5.2.3 Time to Response

Time to response will be calculated for subjects who achieved best overall response of PR, VGPR, CR or sCR. Time to response is calculated as the number of months from the first administration of AMG 420 to the first objective assessment of response (ie, date of the first detection of response) as per IMWG-URC.

Time to response will be descriptively analyzed, summary statistics of the number, mean, standard deviation, median, and range will be reported.

Listings will be produced for all subjects indicating the MRD negativity, OS, PFS, time to response, and duration of response.

9.5.3 Analyses of Exploratory Efficacy Endpoint(s)

9.6 Safety Analyses

9.6.1 Analyses of Safety Endpoint(s)

Statistical analyses on safety endpoints will be done using subjects from the Safety Analysis Set (**except the analysis of the DLT endpoint, which will be based on subjects from the DLT evaluable set**), which includes subjects that are enrolled and received at least 1 dose of AMG 420.

9.6.2 Adverse Events

The Medical Dictionary for Regulatory Activities (MedDRA) version 23.0 or later will be used to code all adverse events to a system organ class and a preferred term. The severity of each adverse event will be graded using CTCAE version 5.0 criteria with exception of CRS which will be graded according to adopted grading system in Lee et al, 2014 and TLS graded according to Cairo-Bishop criteria (refer to protocol Appendix 12). Where appropriate the tables will also be presented by worst grade.

Treatment-emergent adverse events will be summarized based on the number (%) of subjects experiencing events by MedDRA SOC and PT. The denominator for the percentage will be based on the number of subjects in the safety analysis set.

The subject incidence of adverse events will be summarized for

- **TEAE**
 - All treatment-emergent AEs
 - Grade 3 or higher treatment-emergent AEs
 - Treatment-emergent SAEs
 - Treatment-emergent AEs leading to interruption of investigational product
 - Treatment-emergent AEs leading to withdrawal of investigational product
 - Fatal treatment-emergent AEs
- **Treatment-related AEs**
 - All treatment-related AEs
 - Grade 3 or higher treatment-related AEs
 - Treatment-related SAEs
 - Treatment-related AEs leading to interruption of investigational product
 - Treatment-related AEs leading to withdrawal of investigational product
 - Fatal treatment-related AEs

The summaries that are displayed by SOC, PT and grade will be ordered by descending order of incidence of SOC, PT and grade with in each SOC for the total group.

Then summary of TEAEs, summary of TEAEs, TESAEs, Treatment-related TEAEs, and Treatment-related SAEs by SOC, PT and Grade will be generated for extramedullary subjects.

The above adverse event tables will not be created if two or fewer subjects experience the adverse event.

Dose Limiting Toxicities

The analysis of the probability of DLTs will include data from DLT-evaluable subjects (see Protocol Section 7.4.1 for definition of DLT-evaluable). The primary analysis will only include DLTs that occur during the DLT evaluation period. If DLTs occur outside the DLT evaluation period, a sensitivity analysis will be performed where DLTs occurring outside of the specified time interval are included. The number and percentage of subjects reporting DLTs will be evaluated overall and by AMG 420 dose level.

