#### 5.1.1 Phase 1b (Monotherapy Dose Confirmation)

In phase 1b, approximately 10 subjects will be treated at the 400 µg/day dose (comprising cohort 1). Approximately 10 subjects will be treated at the 600 µg/day dose level (cohort 2).

The dose level review team (DLRT) will convene and review all available safety, laboratory, and PK data at the following scheduled time points:

- After at least 10 subjects in phase 1b cohort 1 (400 µg/day dose level) have had the opportunity to complete the 4-week infusion period of the first treatment cycle: On the basis of this review, the DLRT will make a recommendation regarding the initiation of phase 1b cohort 2 (600 µg/day dose level).
- After at least 3 subjects with EM relapsed disease in phase 1b cohort 1 (400 µg/day dose level) have had the opportunity to complete the 4-week infusion period of the first treatment cycle: On the basis of this review, the DLRT will make a recommendation regarding the appropriateness of continued enrollment of subjects

with EM relapsed disease in phase 1b cohort 2 (600 µg/day dose level). Please note that enrollment of subjects with EM relapsed disease in phase 1b cohort 2 will not be allowed until this safety review of the first 3 subjects with EM disease is completed by the DLRT.

- After the first 3 subjects have been dosed with AMG 420 at 600 µg/day for the full 4-week infusion cycle in phase 1b cohort 2.

In phase 1b, the safety data will be reviewed on an ongoing basis and enrollment may be terminated at any time. To further reduce the risk of overdose to ongoing and future subjects, protocol-defined enrollment holding rules will be used. These rules are based on a modified Toxicity Probability Interval (mTPI) (Ji et al, 2010) where the target TPI is a DLT probability from 20% to 33% and the overdose TPI is > 33% DLT probability. Enrollment to the ongoing dose level/schedule will be paused per the rules in [Table 5-1](#) during enrollment into phase 1b cohorts 1 and 2.

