#### 5.4 Justification for Investigational Product Dose (AMG 420)

The primary purposes in phase 1b are to 1) confirm the safety and tolerability of the 400 µg/day dose level in subjects with or without extramedullary (EM) disease and 2) establish the safety and tolerability of the 600 µg/day dose level.

The rationale for dosing in this study is based on the observations and experiences with AMG 420 in the separate FIH study conducted by BI (1351.1), which suggests that a cIV administration is safe and has the potential to induce durable remissions in patients with RRMM. This BI 1351.1 study has identified the 400 µg/day dose level as a preliminary safe and effective dose, as this dose was well tolerated in n = 3 subjects, whereas 2 of 3 subjects treated at the 800 µg/day dose experienced DLTs. The 600 µg/day dose level was not evaluated in the FIH study. Subjects may benefit from higher exposures than are achieved at the 400 µg/day dose level; thus, safety and tolerability of the 600 µg/day dose level may be evaluated in this phase 1b study. The DLRT will convene and review all available safety, laboratory, and PK data from all subjects treated in phase 1b cohort 1 at the 400 µg/day dose before recommending evaluation of the 600 µg/day dose (phase 1b cohort 2). If the DLRT recommends the 600 µg/day dose to be safe and well-tolerated after reviewing the phase 1b cohort 2 data, the sponsor may propose changing the recommended phase 2 dose to 600 µg/day on the basis of interim data analyses.

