The subject identification number must remain constant throughout the entire clinical study; it must not be changed after initial assignment, including if a subject is rescreened.

Enrollment in the study will begin with cohort 1. An Amgen representative will notify the site in writing when cohort 2 is open to screen and enroll subjects. Sites will also be informed as to which cohort their subjects will be allocated to by the Sponsor.

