## **10. Statistical Considerations**

### **10.1 Sample Size Determination**

Approximately 20 subjects will be enrolled (approximately 10 treated at the 400 µg/day dose level and approximately 10 treated at the 600 µg/day dose level).

The sample size is based on practical considerations and it is consistent with the number of subjects enrolled in a dose expansion cohort of a conventional, oncology phase 1 study. With 10 subjects treated at a dose level/schedule, there is a 65% to 89% probability of observing an adverse event if the true event rate is 10% to 20%.

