#### 10.4.2.3 Safety Analyses

##### 10.4.2.3.1 Analyses of Primary Safety Endpoint(s)

Endpoint	Statistical Analysis Methods
Primary	
The primary endpoints are safety endpoints. Unless otherwise specified, statistical analyses on safety endpoints will be done using subjects from the Safety Analysis Set, which includes subjects that are enrolled and received at least 1 dose of AMG 420. Descriptive statistics for safety endpoints will be tabulated overall and by dose level and part.
 
Adverse Events
 
Subject incidence of all treatment-emergent adverse events will be tabulated by system organ class and preferred term. The number and percentage of subjects reporting adverse events will be evaluated overall and by AMG 420 dose level and part will also be tabulated by relationship to AMG 420.
 
Tables of adverse events, fatal adverse events, serious adverse events, adverse events leading to withdrawal from investigational product or other

Endpoint	Statistical Analysis Methods

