7.2 Primary Analysis

The primary analysis will occur when the target enrollment is complete and each subject has had the chance to be treated for at least 6 months.

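### At the primary analysis, by-dose TEAE percentages rest on unequal, uncapped observation time, which can make 600 µg/day look relatively safer than it is for events not confined to cycle 1

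*SAP*

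**What the plan says.** - **Measure.** SAP 9.6.2: "Treatment-emergent adverse events will be summarized based on the number (%) of subjects experiencing events by MedDRA SOC and PT". On the base: "The denominator for the percentage will be based on the number of subjects in the safety analysis set".
- **Layout.** Protocol 10.4.2.3.1: "Descriptive statistics for safety endpoints will be tabulated overall and by dose level and part".
- **Order of cohorts.** Protocol 6.3: "Enrollment in the study will begin with cohort 1". Under Protocol 5.1.1, cohort 2 waits for a DLRT recommendation, made once at least 10 subjects at 400 µg/day "have had the opportunity to complete the 4-week infusion period of the first treatment cycle".
- **Cutoff.** SAP 7.2, where the closing figure is in months: "The primary analysis will occur when the target enrollment is complete and each subject has had the chance to be treated for at least 6". Both cohorts share this trigger. It is a minimum with no upper limit.
- **TEAE window.** SAP section 5 runs it from first dose to 33 days after last dose or end of study, whichever is earlier.
- **Treatment duration.** Protocol 5.3.2 expects a median of about 8 months.
- **Exposure.** SAP 9.6.8 summarizes duration, cycles and dose, but nothing links them to the TEAE tables. No common onset window, rate per unit of time or time-to-first-event summary is planned for TEAEs.

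**The concern.** A crude percentage depends on how long each subject was watched. At the primary analysis every cohort 1 subject could have been observed longer than any cohort 2 subject. Because expected treatment outlasts the 6-month minimum, many cohort 2 subjects will still be on treatment, and so still collecting TEAEs, when the data are cut. The two dose columns would then differ even if the doses were equally toxic.

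TEAEs at 400 and 600 µg/day are among the primary endpoints (Protocol 4.1), and the by-dose tables are what a reader will use. Infections and neurologic events are listed as important potential risks (Protocol Table 3-1), and nothing in the documents confines them to cycle 1. Protocol 5.4 also lets the sponsor propose 600 µg/day as the recommended dose "on the basis of interim data analyses".

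**Working it through.** **1. The plan's own figure.** Protocol 10.1 gives a 65% to 89% chance of seeing an adverse event among 10 subjects at true rates of 10% to 20%. 1 − 0.9^10 = 65.1% and 1 − 0.8^10 = 89.3%, so it reproduces. It concerns one cohort and does not involve observation time.

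**2. Inputs.** From the documents: about 10 subjects per dose, a gap of at least 28 days (28/30.4 = 0.92 month), a 6-month minimum, a 33-day tail and median treatment of about 8 months. Assumed, because the documents are silent: accrual speed, review lag, exponential treatment duration equal at both doses, and a constant event hazard.

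**3. Closed form, time on treatment only.** λ = ln 2/8 = 0.0866 per month. The share still on treatment at 6 months is 2^(−6/8) = 59%. Mean treatment time within t months is (1 − e^(−λt))/λ.
- With instant accrual, t = 6 gives 4.679 and t = 6.92 gives 5.205. The 28-day lead alone puts (5.205 − 4.679)/5.205 = 10.1% of cohort 1 treatment time beyond 6 months.
- With uniform accrual of 4, 2 or 1 subjects per month, the means are 6.95, 8.21 and 9.76 months in cohort 1 against 5.37, 5.97 and 6.95 in cohort 2. Cohort 1 is 29%, 37% and 40% longer, and 33%, 43% and 52% of its time lies beyond 6 months (for example 1 − 4.68/6.95 = 33%).
- Incidence is h/(h+λ) × (1 − e^(−(h+λ)t)), averaged over entry times. If h is solved so that cohort 2 shows 30%, cohort 1 shows 36% to 37% with the same h.

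**4. Simulation with the 33-day tail.** There were 200,000 draws per scenario. The hazard is −ln(0.7)/6 = 0.0594 per month (30% risk over 6 full months), equal at both doses. Pairs are 400/600 µg/day.

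| Accrual per cohort, review lag (months) | Potential follow-up (months) | Crude %, median treatment 8 months | Gap (points) | Crude %, median treatment 3 months | Gap (points) |
|---|---|---|---|---|---|
| 3, 0 | 11.4/7.5 | 35.9/29.3 | 6.6 | 24.4/22.4 | 2.0 |
| 3, 2 | 13.4/7.5 | 38.1/29.3 | 8.8 | 24.8/22.3 | 2.5 |
| 6, 0 | 15.9/9.0 | 39.8/31.9 | 7.9 | 25.2/23.2 | 2.0 |
| 6, 2 | 17.9/9.0 | 41.1/31.9 | 9.2 | 25.3/23.2 | 2.1 |
| 12, 0 | 24.9/12.0 | 43.0/35.4 | 7.6 | 25.4/24.0 | 1.4 |
| 12, 2 | 26.9/12.0 | 43.4/35.4 | 8.0 | 25.5/24.0 | 1.5 |

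**5. Where the gap disappears or changes.**
- Onset within 6 months of first dose: 25.8%/25.8% (8-month median) and 20.8%/20.8% (3-month median).
- Final analysis: 44.4%/44.4% and 25.4%/25.4%.
- Events confined to cycle 1: 30%/30%.
- True hazard ratio of 1.5 for 600 µg/day, 8-month median, no lag: the 6-month window shows 25.8%/35.9%, a gap of 10 points. The crude table shows 35.9%/40.2%, 39.9%/43.1% and 43.1%/46.8%, a gap of only 3 to 4 points.
- Equal hazards, but median treatment of 3 months at 400 and 8 months at 600 µg/day, no lag: the crude table shows 24.4%/29.3% to 25.4%/35.3%, so the direction reverses.

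**6. Scale.** The largest gap, 9.2 points, is 0.92 of a subject in 10. For 3 of 10, the exact 95% interval is 6.7% to 65.2%.

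**The case against.** The strongest reply is that the plan only describes. There is no between-dose contrast, test or hypothesis, and Protocol 10.1 rests the sample size on practical grounds. That stands: a reader might infer that the plan formally compares the doses, and it does not. The side-by-side columns will still be read against each other.

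A reader might also infer that 600 µg/day will necessarily look safer. The documents do not support that. The TEAE window follows treatment, so extra calendar time adds events only for subjects still being treated, and treatment duration by dose is unknown. Step 5 shows a reversal.

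Nor is the primary cutoff the only look at the data. SAP 7.3 plans a final analysis after all subjects have ended the study, and the truncation is gone by then. That does not correct the primary-analysis tables.

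Dose decisions lean mainly on fixed windows: DLTs starting within 28 days, the enrollment-holding rules, and DLRT reviews timed to the first infusion period. In the first-in-human study 10 of 12 CRS events were in cycle 1. SAP 9.6.3 summarizes blood counts by scheduled visit, which gives a time-aligned view of cytopenias. All of this stands and narrows the point to later-onset TEAEs.

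Protocol 5.4 might suggest a still larger imbalance at an interim look. That has not been calculated, SAP 7.1.1 plans no specific interim analysis, and the amendment history records removal of phase 2 and termination of the program.

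**Conclusion.** The point holds in limited form. At the primary analysis, crude by-dose TEAE percentages mix dose with length of observation. For events not confined to cycle 1, with equal hazards and similar treatment duration, the gap against 400 µg/day is about 6 to 9 points at the protocol's expected 8-month median and about 1 to 3 points at a 3-month median. These sizes depend on the assumed accrual, review lag, exponential duration and constant hazard.

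The artefact is under one subject in 10 and small beside the sampling error. It merits correction because it is systematic, affects a primary endpoint, could hide much of a real dose effect, and can be removed with dates already collected.

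**What to change.** In SAP 9.6.2, for the primary analysis:
1. Add by-dose TEAE incidence with onset in cycle 1 (days 1 to 42) and with onset within 6 months of first dose, for all TEAEs, grade 3 or higher, serious TEAEs and infections.
2. Footnote the crude all-time by-dose table as based on unequal observation time.
3. If a rate per patient-month is added, limit it to events not concentrated in cycle 1, such as infections. Time at risk should end at the first event and include the 33-day tail. Applied to all TEAEs it would mislead: an identical 3 of 10 with a cycle 1 event gives 0.3/6.95 = 4.3 against 0.3/5.37 = 5.6 per 100 patient-months, so 600 µg/day would look 29% worse with no difference in risk.

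The cost is SAP wording and a few tables. Late cohort 1 events would appear only in the crude table. The 6-month window removes the truncation, not differences in treatment duration: with medians of 3 months at 400 and 8 months at 600 µg/day and equal hazards it still shows 20.8%/25.8%, so it should be read beside the exposure summary in SAP 9.6.8.

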A phase 1, FIH, open-label, dose escalation study ([1351.1](#)) is ongoing to characterize the safety, tolerability, pharmacokinetics, and pharmacodynamics of cIV doses of AMG 420 in subjects with RRMM. AMG 420 is administered as a cIV infusion for 4 consecutive weeks via an indwelling central IV line. After a 2-week treatment-free

period, the subjects receive up to a total of five 4-week on/2-week off courses. If subjects experience continued benefit, up to 5 more courses may be given.

Data from 35 subjects (up to 800 µg/day) were available at the time of data snapshot (22 May 2018). Subjects were treated at doses ranging from 0.2 µg/day to 800 µg/day. In general, AMG 420 was well tolerated. All 35 subjects (100%) had adverse events; 32 of 35 subjects (91.4%) had adverse events grade ≥ 3. The most frequent adverse events were lymphocyte count decreased (21 subjects, 60.0%); anemia (12 subjects, 34.3%); white blood cell count decreased (12 subjects, 34.3%); pyrexia (11 subjects, 31.4%); and CRS (10 subjects, 28.6%). Infections and infestations occurred in 23 subjects (65.7%), most notably device related infections in 7 subjects (20.0%). Thirty-three of 35 subjects (94.3%) had an adverse event considered drug-related by the investigator. The most frequent drug-related adverse events (> 20%) were lymphocyte count decreased (21 subjects, 60.0%) and CRS (10 subjects, 28.6%). Drug-related grade 3 and grade 4 adverse events occurred in 10 subjects (28.6%) and 17 subjects (48.6%), respectively. The most frequent drug-related grade 3 and grade 4 adverse events were lymphocyte count decreased, with 6 subjects (17.1%) reporting grade 3 events and 14 subjects (40.0%) reporting grade 4 events. No drug-related grade 5 events were reported in this study. Serious adverse events were reported in 17 subjects (48.6%). The most frequent serious adverse events were device-related infections, pneumonia, and cytokine release syndrome (CRS) in 3 subjects (8.6%) each. Most subjects reporting serious adverse events had grade 3 adverse events (12 subjects, 34.3%). Drug-related serious adverse events were CRS in 3 subjects (8.6%), and peripheral motor neuropathy, generalized edema, and pyrexia in 1 subject (2.9%) each. Two dose-limiting toxicities (DLTs) were reported in the 800 µg/day cohort; 1 grade 3 CRS and 1 grade 3 peripheral motor neuropathy.

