9.6.8 Exposure to Investigational Product

The average dose administration (μg), cumulative dose (μg), number of cycles, duration of treatment, number and percentage of subjects with dose modifications, reasons for modification will be summarized using descriptive statistics. Subject-level data may be provided instead of the summary if the subject incidence is low or single dose is given.

Descriptive statistics will be produced to describe the exposure to investigational product by treatment group.

Extent of exposure to study treatments will be summarized for Safety population

- Duration of treatment (days)
 - Defined as the duration (in weeks) from the date of the first dose to the date of the last dose of study drug + 1
- Total number of treatment cycles started
 - Defined as the total number of treatment cycles in which at least one dose of study drug is administered.
- Cumulative dose received of AMG420 across all cycles, defined as the cumulative dose of AMG 420.
- Average dose of AMG420, defined as the total dose received divided by the number of days on treatment administered .

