9.7.5 Analyses of Biomarker Endpoints

The analysis of Biomarker will be described and performed by Clinical Biomarker Group.

10. Changes From Protocol-specified Analyses

There are no changes to the protocol-specified analyses.

11. Literature Citations / References

12. Prioritization of Analyses

No Priority of outputs planned for this study

13. Data Not Covered by This Plan

The analysis of Biomarkers (except MRD) is not covered in this plan.

14. Appendices

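### The SAP drops adverse event tables when two or fewer subjects are affected, although the protocol promises fatal, serious and withdrawal tables with no minimum count

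*SAP*

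**What the plan says.** Protocol 10.4.2.3.1 makes safety the primary endpoint and commits to "Tables of adverse events, fatal adverse events, serious adverse events, adverse events leading to withdrawal from investigational product", among others, without any condition on how many subjects are affected. It adds: "Descriptive statistics for safety endpoints will be tabulated overall and by dose level and part". It also asks for adverse events to be tabulated by relationship to AMG 420.

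SAP 9.6.2 lists six tables for treatment-emergent events: all, grade 3 or higher, serious, leading to interruption, leading to withdrawal, and fatal ("Fatal treatment-emergent AEs"). It repeats the six for treatment-related events and adds tables for subjects with extramedullary (EM) disease. It then says: "The above adverse event tables will not be created if two or fewer subjects experience the adverse event". No category is exempted.

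SAP Section 10 states: "There are no changes to the protocol-specified analyses".

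Elsewhere the SAP does say what happens when numbers are small. For exposure, SAP 9.6.8 says: "Subject-level data may be provided instead of the summary if the subject incidence is low or single dose is given". For efficacy, SAP 9.5.2.3 specifies subject listings. Nothing comparable is given for adverse events.

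**The concern.** The two documents conflict on primary-endpoint outputs, and the SAP says that they do not. With about 20 subjects, one or two deaths, withdrawals or drug-related serious events are 5% to 10% of the study. That is the range in which the rule removes the table. Once the rule exists, the absence of a fatal-event table no longer separates zero deaths from one or two.

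The unit of the rule is also undefined. The SAP does not say whether the threshold applies to a whole table or to a single event term, or whether it is counted per cohort or over both cohorts. Two programmers could produce different outputs from the same text.

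The rule also covers the grade 3 or higher, interruption and EM tables. The protocol does not name these, but EM safety is a stated secondary objective and EM counts will be the smallest in the study.

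**Working it through.** **Inputs**
- n = 20 in total, 10 per dose level (Protocol 10.1; both approximate).
- Event rates of 10% and 20% (Protocol 10.1).
- First-in-human data on 35 subjects (Protocol 3.2.2.4): all 35 had adverse events, 32 had grade 3 or higher events, 33 had drug-related events and 17 had serious events. For drug-related serious events: "Drug-related serious adverse events were CRS in 3 subjects (8.6%), and peripheral motor neuropathy, generalized edema, and pyrexia in 1 subject (2.9%) each". Overlap is not stated, so the number of subjects lies between 3 (full overlap) and 3 + 1 + 1 + 1 = 6 (none), that is 8.6% to 17.1%.
- The documents give no withdrawal or all-cause fatal rate. Rates of 5%, 10% and 20% are assumed for these.

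**Step 1. The protocol's own figure.** Protocol 10.1 gives 65% to 89% for seeing an event at least once in 10 subjects when its true rate is 10% to 20%. P(X ≥ 1) = 1 − (1 − p)^10 gives 1 − 0.9^10 = 0.651 and 1 − 0.8^10 = 0.893. The figure reproduces.

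**Step 2. Whole-table reading, pooled, n = 20.** A table is lost despite affected subjects when X is 1 or 2:

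P(1 ≤ X ≤ 2) = 20p(1 − p)^19 + 190p²(1 − p)^18

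| Rate p | P(X = 1) | P(X = 2) | Table dropped despite events |
|---|---|---|---|
| 3/35, drug-related serious, lower | 0.3123 | 0.2782 | 0.5905 |
| 6/35, drug-related serious, upper | 0.0963 | 0.1892 | 0.2854 |
| 17/35, all serious | <0.0001 | 0.0003 | 0.0003 |
| 5%, assumed | 0.3774 | 0.1887 | 0.5660 |
| 10%, assumed | 0.2702 | 0.2852 | 0.5554 |
| 20%, assumed | 0.0577 | 0.1369 | 0.1946 |

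(Sums were taken before rounding.) At 32/35, 33/35 or 35/35 the chance of two or fewer affected subjects among 20 is negligible. The all-event, all-related and grade 3 or higher tables therefore survive on this reading.

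**Step 3. Event-level reading.** If the threshold applies to each term, the term is shown only when X ≥ 3.

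| n | Rate | P(X ≥ 1), no minimum | P(X ≥ 3), SAP rule |
|---|---|---|---|
| 10 | 10% | 0.651 | 0.070 |
| 10 | 20% | 0.893 | 0.322 |
| 20 | 10% | 0.878 | 0.323 |
| 20 | 20% | 0.988 | 0.794 |

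On this reading, counted per cohort, the protocol's 65% to 89% becomes 7% to 32% for an event being tabulated.

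**Step 4. EM serious-event table.** The number of EM subjects is not fixed. At the all-serious rate of 17/35, P(1 ≤ X ≤ 2) is 0.749 for 3 EM subjects, 0.352 for 6 and 0.064 for 10. With 3, the number needed for the dose level review, all three must be affected before the table is produced.

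**The case against.** The strongest objection concerns scope. The sentence comes directly after the EM paragraph, so the tables it refers to could be the EM tables alone. The overall fatal, serious and withdrawal tables would then be safe, and the Section 10 statement could be taken as confirming that. This reading is possible but less literal, because the sentence limits itself to nothing. Even on this reading, the tables for a secondary objective would be lost where counts are smallest.

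Second, the loss is bounded. On the whole-table reading, Step 2 shows that the all-event, all-serious, all-related and grade 3 or higher tables survive at first-in-human rates. DLT counts, reasons for ending treatment and overall survival are outside the rule, and a worst-grade table, which the SAP makes optional, could show grade 5 terms. The dose level review is unaffected. This stands. What would be lost is withdrawals and deaths by term and the cross-classification of serious by related. The protocol names the first two. It asks for tabulation by relationship but does not name a treatment-related serious table.

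Third, the rates are uncertain. The first-in-human figures pool doses from 0.2 to 800 µg/day, while this study uses 400 and 600. Protocol 7.4.2.1.3 makes a DLT grounds for permanent discontinuation unless an exception applies, and the target DLT interval is 20% to 33%, so withdrawals may be commoner than 5% or 10%. At 20%, 25% and 33% the drop probability is 19%, 9% and 2%. That affects the size of the problem, not the conflict of wording.

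Finally, for one or two subjects a listing carries at least as much information as a table. But the SAP specifies no adverse event listing, and the protocol promises tables.

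**Conclusion.** The concern holds. Followed as written, the SAP suppresses primary-endpoint tables that the protocol promises unconditionally, offers nothing in their place, and declares no departure. The conflict lies in the wording and does not depend on any assumed rate.

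The tables most exposed are withdrawal, fatal and treatment-related serious. For the last, the chance of losing the table despite affected subjects is 59% to 29%, provided that first-in-human rates carry over, the threshold applies to whole tables and counts are pooled over 20. For withdrawals and deaths the size rests on assumed rates. The event-level figures apply only if the threshold is meant per term, which the SAP leaves open.

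The SAP cites protocol amendment 4 and the protocol supplied is amendment 5. The amendment 5 rationale does not mention Section 10.4.2.3, so nothing in the documents suggests that the version gap explains the mismatch. This must be fixed.

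**What to change.** Delete the sentence from SAP 9.6.2. Produce every listed table whatever the count, overall, by dose level and for EM subjects, showing a zero where no subject is affected. Subject-level listings for rare categories are useful, but should be added to the tables and not replace them. Section 10 of the SAP then needs no change on this point. If the sponsor prefers listings in place of tables for counts of one or two, that departs from the protocol: it would have to be declared in Section 10, with the unit of the threshold defined.

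The cost is one deleted sentence and a few short extra tables. Data collection, the DLT analysis and the dose level review are unchanged.
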